## 2. Synopsis

### Study Rationale

Transforming growth factor beta (TGF- $\beta$ ) is an important protein that regulates the immune response to tumor cells and metastatic spread of tumor cells. TGF- $\beta$  is also an important regulator of neoangiogenesis. LY2157299 is a small molecule designed to selectively inhibit the serine/threonine kinase of the TGF- $\beta$  receptor type I (RI). Thus, the antitumor effect of a TGF- $\beta$  inhibitor such as LY2157299 is expected to result in an increased tumor immune surveillance, reduced metastatic spread, and decreased tumor-associated neoangiogenesis. The role of TGF- $\beta$  inhibitors in hepatocellular carcinoma (HCC) was investigated in several in vitro and in vivo studies. For example, the TGF- $\beta$  RI inhibition by LY2109761 produced several different antitumor activities in HCC preclinical models. The spread of HCC cells in the surrounding tissue is inhibited by the up-regulation of E-cadherin (Fransvea et al. 2008). LY2109761 inhibits invasion of HCC cells (Fransvea et al. 2009) and also inhibits tumor growth thanks to inhibition of neoangiogenesis by reducing vascular endothelial growth factor production (Mazzocca et al. 2009). These effects are selectively dependent on the TGF-1/SMAD-2 pathway (Melisi et al. 2008; Zhang 2009). Finally, LY2109761 inhibits the production of connective tissue growth factor, interrupts the cross talk between tumor and stroma, and blocks the progression of HCC (Mazzocca et al. 2010). Inhibition of TGF- $\beta$  RI activation using LY364947 inhibits TGF- $\beta$ -dependent cell signaling and reduces cell motility and invasion in parental and multikinase-resistant HCC cells (Garbay et al. 2010).

The scientific justification of investigating LY2157299 in HCC is compelling based on the role of TGF- $\beta$  in the process of fibrosis and cirrhosis leading to HCC. The evidence of antitumor effects in several preclinical models with TGF- $\beta$ -dependent tumor growth and their inhibition by other TGF- $\beta$  inhibitors, such as LY2109761 and LY364947, suggest that LY2157299 will have activity in HCC. Preclinical data of the combination of LY2157299 and sorafenib shows the potentiation of sorafenib activity in vitro and ex vivo study and implies the possibility that this combination may be more effective than sorafenib alone. In addition, clinical data from HCC patients who have progressed on sorafenib and were treated with LY2157299 had antitumor activity (Study H9H-MC-JBAK [JBAK]). Based on recent interim analysis including 106 patients from Study JBAK, which studied LY2157299 in HCC, treatment resulted in a median time-to-tumor progression (TTP) of 12 weeks (18.3 weeks in patient without previous sorafenib treatment) and alpha fetoprotein (AFP) responses (as defined by >20% reduction from baseline) in 22% of patients.

The present Phase 2 study will further explore the safety and efficacy of LY2157299 alone or in combination with sorafenib in Asian patients with HCC who have not received prior systemic treatment for advanced disease.

**Clinical Protocol Synopsis: Study H9H-MC-JBAS**

Name of Investigational Product: LY2157299 Monohydrate (hereafter referred to as LY2157299)	
Title of Study: A Randomized Phase 2 Study of LY2157299 versus LY2157299 – Sorafenib Combination versus Sorafenib in Patients with Advanced Hepatocellular Carcinoma	
Number of Planned Patients: Entered: Approximately 150 patients Enrolled/randomly assigned: 120 patients Completed: 100 deaths	Phase of Development: 2
Length of Study: approximately 30 months Planned first patient visit: April 2014 Planned last patient visit: January 2017 Planned interim analyses: #1: approximately 10 patients complete Cycle 1 in LY2157299 monohydrate (hereafter referred to as LY2157299) plus sorafenib arm; #2: 32 patients are randomized and complete 3 cycles of treatment, discontinue from study drug, or die; #3: 70 total deaths	
Objectives: The primary objective of this study is to compare the overall survival (OS) distributions between LY2157299 plus sorafenib therapy and sorafenib plus placebo therapy (control arm) in patients who have not received prior systemic treatment for advanced disease.  The secondary objectives of the study are: 
 
• to estimate the hazard ratio (HR) from the OS distributions between LY2157299 monotherapy and sorafenib plus placebo
 
• to evaluate the safety of LY2157299 as monotherapy and in combination with sorafenib in HCC patients
 
• to evaluate the population pharmacokinetics (PK) of LY2157299 as monotherapy and in combination with sorafenib in HCC patients
 
• to characterize other time-to-event distributions, such as TTP and progression-free survival (PFS), based on Response Evaluation Criteria in Solid Tumors [RECIST] version 1.1
 
• to estimate antitumor efficacy using objective response rate (ORR, based on RECIST version 1.1 and modified RECIST [mRECIST]) for each treatment arm
 
• to assess patient-reported outcome (PRO) measures of disease-specific symptoms, time to symptomatic progression, and health-related quality of life questionnaires such as the European Organisation for Research and Treatment of Cancer (EORTC) quality-of-life questionnaire (QLQ)-30 and QLQ HCC-18 for each treatment arm
 
 The exploratory objectives of this study are: 
 
• to explore markers associated with EMT transformation and the TGF-<math>\beta</math>-associated signaling pathway presence in the original diagnostic tumor tissue and optional posttreatment tumor tissue and the correlation of this with both clinical efficacy endpoints and biomarker response
 
• to explore TTP, PFS, and ORR by immune response RECIST (irRECIST)
 
• to explore tumor volume changes of measurable lesions on CT/MRIs obtained for tumor response as an assessment of treatment effects on biological growth rate
 
• to explore the relative effects of LY2157299 versus LY2157299 plus sorafenib versus sorafenib plus placebo on antiangiogenesis as assessed by dynamic contrast-enhanced magnetic resonance imaging (DCE-MRI) metrics and on tumor cellularity/cell death as assessed by diffusion-weighted magnetic resonance imaging (DW-MRI) metrics. These exploratory magnetic resonance imaging (MRI) techniques will only be performed at clinical sites where the associated MR imaging center scanner has been qualified prior to patient enrollment by the imaging core laboratory designated by the sponsor.
 
• to explore fibrosis-related tests, such as fibrotest
 
• to assess healthcare resource utilization including transfusions and hospitalizations
 
	

**Study Design:** This is a 3-arm, 1:2:1 randomized, multicenter, global (Asia), Phase 2 study of LY2157299 monotherapy or LY2157299 plus sorafenib therapy compared to sorafenib plus LY2157299-matched placebo therapy in patients with relapsed or progressed HCC. Patients who receive sorafenib and investigators will be blinded to the LY2157299 or placebo assignment for those arms.

**Diagnosis and Main Criteria for Inclusion and Exclusions:**

**Inclusion Criteria:**

- have histological evidence of a diagnosis of HCC not amenable to curative surgery.
- have Child-Pugh Class A
- have the presence of measurable disease as defined by RECIST version 1.1. A lesion that has been previously treated by local therapy at least 3 weeks prior to the baseline scan will qualify as a measurable or evaluable lesion if there was demonstrable progression following locoregional therapy
- be aged  $\geq 18$  years
- have adequate organ function
- have a performance status of  $\leq 1$  on the Eastern Cooperative Oncology Group (ECOG) scale
- have available diagnostic or biopsy tumor tissue

**Exclusion Criteria:**

- have received previous systemic treatment for advanced disease
- have known HCC with fibro-lamellar or mixed histology
- have presence of clinically relevant ascites
- have had liver transplant
- have moderate or severe cardiac disease
- have known hypersensitivity to sorafenib or its excipients
- have active or uncontrolled clinically serious hepatitis B virus or hepatitis C virus infection
- have experienced any Common Terminology Criteria for Adverse Events (CTCAE) Grade 3 or 4 gastrointestinal bleeding or any variceal bleeding episode in the 3 months prior to enrollment requiring transfusion or endoscopic or operative intervention
- have esophageal or gastric varices that require immediate intervention (eg, banding, sclerotherapy) or represent a high bleeding risk in the opinion of the investigator or consulting gastroenterologist or hepatologist

**Test Product, Dosage, and Mode of Administration**

LY2157299 will be administered orally by daily dosing morning and evening (twice daily [BID]). The monotherapy dose will be 150 mg BID (300-mg daily dose) for 14 days, followed by 14 days with no study drug. The LY2157299 dose used in combination with sorafenib will be determined based on the results of the H9H-MC-JBAK (JBAK) study Part C (dose will either be 80 mg or 150 mg BID [160 mg or 300 mg daily dose]) for 14 days, followed by 14 days with no study drug.

LY2157299-matched placebo will be administered orally by daily dosing morning and evening (BID) for 14 days, followed by 14 days with no placebo.

Sorafenib will be administered orally by daily dosing morning and evening (BID) at 400 mg per dose (total dosage of 800 mg daily) for 28 days.

One cycle is defined as 28 days in all treatment arms.

**Planned Duration of Treatment Per Patient:** Patients will receive LY2157299 until their disease has progressed, the patient has died, or the patient discontinues for adverse events, investigator's judgment, or other reasons.

**Wash-out period:** none.

**Planned Follow-up Observation Period Per Patient:** Patients who have discontinued study treatment without progression will continue to be followed for progression. Every attempt should be made to gather all information every 2 months (radiological scans and survival), even if a patient starts a new anticancer therapy. All patients will be followed until death. Patients who have entered the treatment extension period will be followed for just 30 days after treatment discontinuation.

**Criteria for Evaluation:**

Efficacy: OS, TTP, PFS, and ORR using RECIST version 1.1, mRECIST, and irRECIST

Safety: International CTCAE, version 4.0

Health Outcomes: PRO measures of disease-specific symptoms and health-related quality of life (EORTC QLQ-30 and QLQ HCC-18)

Bioanalytical: Plasma LY2157299/sorafenib concentrations will be analyzed by liquid chromatography/mass spectrometry/mass spectrometry.

**Statistical Methods:**

Statistical: Approximately 120 patients will be randomly allocated to treatment in a 1:2:1 ratio (LY2157299 monotherapy/LY2157299 plus sorafenib therapy/sorafenib plus placebo therapy). This will provide about 83% power (strong prior) to detect a significant treatment difference in terms of OS between the LY2157299 plus sorafenib and sorafenib plus placebo using a Bayesian-augmented control design with a 1-sided alpha of 0.14 under the assumption that the true HR is 0.667 in favor of the LY2157299 plus sorafenib arm.

Efficacy: The primary analysis is to compare the OS between LY2157299 plus sorafenib with sorafenib plus placebo using a Bayesian OS model that augments current control data with additional information from historical data. The same Bayesian OS model will be used to estimate the HR between LY2157299 monotherapy and sorafenib plus placebo. HRs between the 3 treatment arms will also be estimated for TTP and PFS using proportional hazards models. ORR based on the RECIST v1.1 and mRECIST criteria will be calculated.

Safety: Summary statistics, plots, and listings for all safety data collected will be provided by arm.

Health Outcomes: Summary descriptive statistics by study part will be provided for the PRO data (ie, EORTC QLQ-30 and QLQ HCC-18) at each time point and change from baseline. Time to symptomatic progression will also be evaluated.

Pharmacokinetics: A population PK analysis will be performed on all patients receiving LY2157299. A PK analysis will be performed for sorafenib as well. This analysis will explore the impact of covariates such as demographic factors and markers on the relevant PK parameters.

Pharmacodynamics: Changes in response biomarkers, such as phosphorylated SMAD in tumor tissue (or other TGF- $\beta$ -related biomarkers), AFP L3, and E-cadherin in serum will be estimated and may be correlated with clinical efficacy. Exploratory population PK/pharmacodynamic analyses may be conducted to identify the exposure-biomarker response relationship.

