The ability of LY2157299 to inhibit CYP-mediated metabolism *in vitro* was examined. The data show that LY2157299 would not be expected to inhibit metabolism mediated by CYP2D6, CYP2C19, CYP2C9, and CYP1A2. LY2157299 was found to competitively inhibit the biotransformation of midazolam to 1'-hydroxymidazolam, a marker activity for CYP3A4, yielding an inhibition constant value of 44  $\mu\text{M}$ . LY2157299 was found to competitively inhibit the biotransformation of testosterone to 6 $\beta$ -hydroxytestosterone, a marker activity for CYP3A4, yielding an inhibition constant value of 290  $\mu\text{M}$ .

Based on the nonclinical metabolism studies, LY2157299 is not anticipated to have the potential to accumulate in patients or have a risk of high hepatic metabolism.

For details on the nonclinical PK of LY2157299, please see the Investigator's Brochure (IB).

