## **9.6. Concomitant Therapy**

Except for GnRH-agonist therapy and antiestrogen therapy (if patients are stable on these therapies), no other anticancer therapy, immunotherapy, hormonal cancer therapy, herbal treatment as anticancer treatment or experimental medications will be permitted while the patients are participating in this study. Palliative radiation therapy to nontarget lesions is allowed. Any disease/symptomatic progression requiring other forms of specific antitumor therapy will be cause for early discontinuation of study therapy.

The use of antiviral therapy should be considered in accordance with local guideline or American Association for the Study of Liver Diseases practice guidelines or in consultation with hepatitis experts (Lok and McMahon 2009).

During the first-in-human Study JBAH, patients received enzyme-inducing anti-epileptic drugs, such as carbamazepine, phenobarbital, or phenytoin. No apparent drug-drug interaction has been observed, consistent with the nonclinical absorption, distribution, metabolism, excretion properties of this agent.

When sorafenib is administered, avoid concomitant use of strong CYP3A4 inducers (such as, carbamazepine, dexamethasone, phenobarbital, phenytoin, rifampin, rifabutin, St. John's wort),

when possible, because inducers can decrease the systemic exposure to sorafenib. Warfarin is not recommended for coadministration with sorafenib.

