### **10.4.3. Samples for Drug Concentration Measurements Pharmacokinetics**

Sparse samples for PK evaluation will be collected from all patients in the study as indicated in [Attachment 5](#). The actual time of dosing on the day of sampling and the actual time of sampling for each of the samples must be collected. Dose information (dose time and amount of dose) must be collected for the day of sampling and the 2 days prior to the sampling day. This information can be obtained from the patient at the visit for blood sampling.

The sampling times in the schedule are approximate, and the actual sampling time should be recorded. Instructions for the collection and handling of blood samples will be provided by the sponsor.

Plasma PK samples will be collected and analyzed for LY2157299 and sorafenib using a validated method. PK samples for the LY2157299-matched placebo may be collected but will not be analyzed. A maximum of 8 samples may be collected at additional time points during the study if warranted and agreed upon between both the investigator and Lilly.

Drug concentration information will not be reported to investigative sites or blinded personnel.

Bioanalytical samples collected to measure study-drug concentration will be retained for a maximum of 2 years following the last patient visit for the study.

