### **12.2.8. Pharmacokinetic Analyses**

The plasma-concentration-versus-time data together with information on dosing and patient characteristics will be pooled and analyzed using a population PK analysis approach. Nonlinear mixed-effect modeling (NONMEM) will be used for the estimation of the population PK parameters of LY2157299. Sorafenib PK will be assessed against a published sorafenib population PK model.

All patients who have completed at least 2 days of sampling will be included in the PK analysis. LY2157299 PK will be modeled using NONMEM. These population parameters will describe the average dose-concentration relationship in the target population, the influence of fixed effects

(such as weight or age) on a PK parameter of interest, the interindividual variation in the PK parameter, and the residual variation in the observed concentration.

For the purposes of the JBAS clinical study report, plasma-concentration data will be illustrated graphically and summarized descriptively. If data is sufficient, then data from patients in this study will be modeled using the population approach for characterizing LY2157299 PK.

Exploratory PK/PD analyses will be conducted to identify the exposure-response (biomarker) relationship in this study. The PK and PK/PD analyses may be reported as separate stand-alone reports for this study. Additional analyses such as exposure-response using TTP and/or other appropriate clinical endpoints may be explored, if data warrant.

The version of any software used for the analysis will be documented, and the program will meet Lilly requirements for software validation. It is possible that other validated equivalent PK software programs may be used if appropriate, warranted, and approved by global PK management.

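### The only stated reference for sorafenib PK is a published external model; the randomised Arm 2 versus Arm 3 contrast of sorafenib exposure is available but not specified

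*Protocol*

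**What the plan says.** The Pharmacokinetics entry of the synopsis states "A PK analysis will be performed for sorafenib as well" and continues "This analysis will explore the impact of covariates such as demographic factors and markers on the relevant PK parameters". It names no reference model and no comparator.

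The method appears in Protocol 12.2.8 and, in the same words, in SAP 6.11.1: "Sorafenib PK will be assessed against a published sorafenib population PK model". In both sections NONMEM estimation is described for LY2157299 only.

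On sampling, Protocol 10.4.3 says "Sparse samples for PK evaluation will be collected from all patients in the study as indicated in" Attachment 5, and then "Plasma PK samples will be collected and analyzed for LY2157299 and sorafenib using a validated method". The next sentence adds "PK samples for the LY2157299-matched placebo may be collected but will not be analyzed".

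Attachment 5 gives one schedule for everyone. Its footnote drops the Day 14 evening dose of LY2157299 or placebo, and of sorafenib. Arms 2 and 3 are randomised (Protocol 9.3), blinded to LY2157299 or placebo (9.5) and planned at 60 and 30 patients (12.1).

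**The concern.** The trial contains the clean experiment: same sorafenib regimen, same sampling times, random allocation, LY2157299 or placebo added. The plan instead names an outside benchmark. If Arm 2 alone were compared with that benchmark, a gap could come from LY2157299, from differences in population or liver function, or from the assay.

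The documents give some reason to look. Protocol 5.1.1 reports that in vitro "LY2157299 was found to competitively inhibit the biotransformation of midazolam", a CYP3A4 marker reaction. Protocol 9.6 warns, of strong CYP3A4 inducers, that "inducers can decrease the systemic exposure to sorafenib". Neither shows a clinical interaction, but the documents contain no clinical data on what LY2157299 does to sorafenib exposure.

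At stake is the reading of Arm 2 against Arm 3. Protocol 8.2 wants the three arms to differentiate safety profiles and inform Phase 3. If toxicity is higher in Arm 2, the team will want to know whether sorafenib exposure was also higher.

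**Working it through.** **1. Is a between-arm sorafenib comparison specified anywhere?**

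- Protocol 6.2: the PK objective covers LY2157299 only.
- Protocol 5.2: the one within-trial PK comparison is LY2157299 in combination versus LY2157299 alone.
- Protocol 12.2.13: interim analysis 1 looks at PK and safety in the combination arm.
- Synopsis: the covariate examples are demographic factors and markers. The list is open-ended, but co-administration is not on it.
- Protocol 12.2.8 and 12.2.1: concentrations are to be plotted and summarised descriptively, and descriptive results are shown by arm. This gives by-arm summaries but no ratio or interval.

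So by-arm description is planned and an estimated contrast is not.

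**2. Does the sampling support the contrast?**

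Attachment 5 has Cycle 1 Day 14 samples predose, at 0.5-2 h and at 3-5 h, then Day 15 morning before sorafenib. These fall at the end of the LY2157299 dosing period. Cycle 1 Day 22 (labelled morning, not predose) and Cycle 2 Day 1 predose fall in the off period. With a median LY2157299 half-life of 6 to 8 h (Protocol 5.1.3), the gap from the Day 14 morning dose to Day 22 is 8 × 24 = 192 h, or at least 192/8 = 24 half-lives. On and off conditions can therefore both be compared between arms. Protocol 10.4.3 requires actual dosing and sampling times to be recorded.

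**3. How precise would it be?**

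The documents state no sample size, power or precision for sorafenib PK, so there is no planned figure to reproduce. They also give no between-patient CV for sorafenib. The range 40% to 100% is an assumption; the nearest figure in the documents is 42% for LY2157299 CL/F in HCC (Protocol 5.1.3).

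Assume log-normal exposure:

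- SD of log exposure = √ln(1 + CV²)
- SE of the log ratio = SD × √(1/60 + 1/30) = SD × 0.2236
- 90% CI factor = exp(1.645 × SE)
- ratio detectable with 80% power, two-sided 5% = exp((1.96 + 0.8416) × SE)

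| Assumed CV | SD (log) | SE | 90% CI factor | Detectable ratio |
|---|---|---|---|---|
| 40% | 0.385 | 0.086 | 1.15 | 1.27 |
| 60% | 0.555 | 0.124 | 1.23 | 1.42 |
| 80% | 0.703 | 0.157 | 1.30 | 1.55 |
| 100% | 0.833 | 0.186 | 1.36 | 1.68 |

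If 20% of patients were not evaluable (48 versus 24, also assumed), the multiplier becomes √(1/48 + 1/24) = 0.25. The CI factors for CVs of 60%, 80% and 100% become 1.26, 1.34 and 1.41.

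**The case against.** Several points on the other side stand.

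- **Not inseparable.** A reader might infer that an effect of LY2157299 on sorafenib cannot be separated from population differences. The documents do not support that. If both sorafenib arms are set against the same model, those differences are common to both and the between-arm gap isolates LY2157299. The on and off samples within Arm 2 offer a second route.
- **The detailed plan is elsewhere.** SAP 6.11 describes its PK text as informational and defers to a PK/pharmacodynamic analysis plan that was not available for review. That plan may already contain the comparison. Protocol 12.2.8, however, carries no such caveat and names only the external model.
- **Placebo-arm assays.** The sentence "PK samples for the LY2157299-matched placebo may be collected but will not be analyzed" might be taken to mean that Arm 3 is never assayed for sorafenib. Read with the sentence before it, the natural meaning is that only the LY2157299 assay is skipped. The wording is loose rather than wrong.
- **An interaction may be small.** The in vitro inhibition constants are 44 and 290 µM (Protocol 5.1.1). At 300 mg/day and CL/F 25.4 L/h (Protocol 5.1.5.1), average concentration is 300/25.4/24 = 0.49 mg/L. For an assumed molecular weight of 300 to 500 g/mol (not in the documents) that is 1.0 to 1.6 µM, or 2% to 4% of the lower constant. This is a systemic average and does not address peaks or the gut wall.
- **No bias in survival.** A reader might infer that an exposure change would bias the OS comparison. It would not. The trial compares adding LY2157299 with adding placebo, and any change in sorafenib exposure is part of that effect.
- **Cross-population drift.** LY2157299 clearance differed between glioblastoma and HCC by 38.4/25.4 = 1.51-fold (Protocol 5.1.5.1). This illustrates that PK can shift between populations, but it concerns another drug and says nothing about the size of any mismatch with a sorafenib model.

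What remains is that the only method named is the weaker one, while a better one is already built into the design.

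**Conclusion.** The point holds as a specification gap and an inexpensive improvement. Protocol 12.2.8 and SAP 6.11.1 name an external model as the sole reference for sorafenib PK and specify no estimate of the difference in sorafenib exposure between Arms 2 and 3. The design does not prevent that estimate.

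The contrast would be informative, though not definitive for small effects: a 90% CI factor of about 1.15 to 1.36, and 80% power for exposure ratios of about 1.27 to 1.68. These figures assume log-normal exposure, a sorafenib CV of 40% to 100% and all 60 and 30 patients evaluable. They also take no account of sorafenib dose reductions, omissions or dropout before sampling.

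The primary OS analysis is unaffected. The gain lies in interpreting toxicity and efficacy differences between Arms 2 and 3.

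**What to change.** 1. **Protocol 12.2.8 and SAP 6.11.1** (and the PK/pharmacodynamic analysis plan, if it does not already say so): make Arm 2 versus Arm 3 the main sorafenib PK analysis. Either fit one population model to both arms with LY2157299 co-administration as a covariate on sorafenib CL/F, or report a dose-adjusted geometric mean ratio of exposure with 90% CI. Keep the published model as the structural starting point.
2. **Samples:** cover Cycle 1 Days 14-15 (LY2157299 on), and Cycle 1 Day 22 morning and Cycle 2 Day 1 predose (LY2157299 off). Use actual dosing and sampling times, since Day 22 is not designated predose. Adjust for the sorafenib dose taken, since Protocol 9.1 and 9.4.1.2 allow reduced doses.
3. **Protocol 10.4.3:** state that Arm 3 samples are assayed for sorafenib and that only the LY2157299 assay is omitted.

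The cost is wording, one extra secondary analysis and, at most, sorafenib assays on samples already scheduled from about 30 Arm 3 patients.
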